4.1.1 Inclusion Criteria

Patients must meet the following criteria for study entry:

1. Male and female patients aged 40–80 years, inclusive.
2. Clinical symptoms consistent with IPF of ≥ 6 months duration.
3. Patients should have both “confident” or “consistent” with UIP diagnosis of IPF based on clinical, radiologic or pathologic data according to 2011 ATS/ERS guidelines at the Screening. HRCT scan performed within 24 months before the start of the Screening may be used.
4. No features supporting an alternative diagnosis on transbronchial biopsy, bronchoalveolar lavage (BAL), or surgical lung biopsy, if performed. Results of the surgical lung biopsy performed within the last 4 years must be confirmed by central review.
5. Patients with %FVC ≥ 40 % at the Screening.
6. Patients with %DL_{CO} ≥ 30 % at the Screening.
7. Ability to walk ≥ 100 m during the 6-minute walk test at the Screening.
8. Eligible patients must discontinue all prohibited medications at least 28 days before the *start of treatment*.
9. Female patients of childbearing potential must have negative urine pregnancy test at the Screening and before first dosing on Day 1.

Pirfenidone—F. Hoffmann-La Roche Ltd

10. Patients able to conceive must agree to use safe contraceptive methods for the whole duration of the study and 28 days after the last dosing.

- a. For women of childbearing potential: agreement to remain abstinent (refrain from heterosexual intercourse) or use a highly effective contraceptive method with a failure rate of < 1% per year during the treatment period and for at least 28 days after the last dose of pirfenidone. A woman is considered to be of childbearing potential if she is postmenarcheal, has not reached a postmenopausal state (≥ 12 continuous months of amenorrhea with no identified cause other than menopause), and has not undergone surgical sterilization (removal of ovaries and/or uterus). Examples of highly effective contraceptive methods with a failure rate of < 1% per year include bilateral tubal ligation, male sterilization, hormonal contraceptives that inhibit ovulation, hormone-releasing intrauterine devices (IUD), and copper intrauterine devices.
- b. For men: agreement to remain abstinent (refrain from heterosexual intercourse) or use contraceptive measures, and agreement to refrain from donating sperm, as defined below:

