- b. aspartate or alanine aminotransferase (AST or ALT) > 3 × ULN;
- c. alkaline phosphatase > 2.5 × ULN.

23. Creatinine clearance < 30 mL/min, calculated using the Cockcroft-Gault formula (see [Section 4.5.8](#)).

24. Electrocardiogram (ECG) with a QT interval corrected according to Fridericia's formula (QTcF) > 500 msec at the Screening.

Other Exclusions:

25. Inability to return for follow-up visits or obtain follow-up data required to assess study therapy, or presence of other reasons for anticipated non-compliance to therapy or procedures, in the opinion of the investigator.

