4.5.8 Laboratory, Biomarker, and Other Biological Samples

All samples for laboratory tests (hematology, blood chemistry, serologic tests) will be analyzed in the study site's local laboratory.

Blood samples should be obtained in fasted patients and handled appropriately. The following parameters will be utilized in the study:

- hematology (plasma): white blood cells (WBC) count, red blood cells (RBC) count, hemoglobin, hematocrit, platelet count, (relative) differential WBC count (neutrophils, eosinophils, basophils, monocytes, lymphocytes);
- blood chemistry panel (serum or plasma): albumin, alkaline phosphatase (AP), ALT, AST, direct bilirubin, total bilirubin, total protein, albumin, cholesterol, creatine kinase (CK), creatinine, triglycerides, gamma-glutamyl transferase

Pirfenidone—F. Hoffmann-La Roche Ltd

(GGT), glucose, lactic dehydrogenase (LDH), calcium, phosphorus, magnesium, potassium, sodium, urea nitrogen, uric acid;

- serologic tests (at screening only, exclusion tests): rheumatoid factor, anticyclic citrullinated peptide and antinuclear antibody titer.

Creatinine clearance

Creatinine clearance should be assessed at the Screening for eligibility confirmation using the following formula by Cockcroft-Gault (Cockcroft DW et al, 1976):

For serum creatinine concentration in mg/dL:

$$\text{CrCl (mL/min)} = (140 - \text{age (years)}) \times \text{weight (kg)} \times 1.0 / 72 \times \text{serum creatinine (mg/dL)}$$

For serum creatinine concentration in $\mu\text{mol/L}$:

$$\text{CrCl (mL/min)} = (140 - \text{age (years)}) \times \text{weight (kg)} \times 1.0 / 0.81 \times \text{serum creatinine (\mu mol/L)}$$

Pregnancy test

All women of childbearing potential will have a urine pregnancy test at the Screening and on Day 1 before start of treatment. Only women with negative pregnancy test will be included in the study. Urine pregnancy tests will be performed repeatedly at specified subsequent visits as scheduled in the [Appendix 1](#).

If a urine pregnancy test is positive, it must be confirmed by a serum pregnancy test. Women with confirmed positive pregnancy test should be immediately withdrawn from the study treatment (see [Section 5.4.3](#)). Urine pregnancy test will be performed by the investigator using test-strips with least sensitivity to human chorionic gonadotropin (hCG) of 10 mLU/mL.

The investigator can perform clinical laboratory assessments more frequently, if it is clinically indicated.

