9.4. Clinical Laboratory Evaluations

eCRF form: “HEMATOLOGY”, “SERUM CHEMISTRY”.

Clinical laboratory evaluations as scheduled in the Table 1 include the following parameters:

- hematology (plasma): white blood cells (WBC) count, red blood cells (RBC) count, hemoglobin, hematocrit, platelet count, (relative) differential WBC count (neutrophils, eosinophils, basophils, monocytes, lymphocytes);
- blood chemistry panel (serum or plasma): albumin, alkaline phosphatase (AP), ALT, AST, direct bilirubin, total bilirubin, total protein, cholesterol, creatine kinase (CK), creatinine, triglycerides, gamma-glutamyl transferase (GGT), glucose, lactic dehydrogenase (LDH), calcium, phosphorus, magnesium, potassium, sodium, urea nitrogen, uric acid;

Creatinine clearance should be assessed at the Screening for eligibility confirmation using the following formula by Cockcroft-Gault (Cockcroft DW et al, 1976):

For serum creatinine concentration in mg/dL:

ML39355_STATISTICAL ANALYSIS PLAN_Final 2.0_17 June 2020

$$\text{CrCl (mL/min)} = (140 - \text{age (years)}) \times \text{weight (kg)} \times 1.0 / 72 \times \text{serum creatinine (mg/dL)}$$

For serum creatinine concentration in $\mu\text{mol/L}$:

$$\text{CrCl (mL/min)} = (140 - \text{age (years)}) \times \text{weight (kg)} \times 1.0 / 0.81 \times \text{serum creatinine } (\mu\text{mol/L})$$

For laboratory parameters the following tables will be presented according to section 7:

- descriptive statistics of measured values and changes from baseline (including creatinine clearance);
- shift tables based on comparison with normal range (Lower/Normal/Higher);
- frequency tables for Out of range: No/Yes clinically significant (Yes CS) / Yes non-clinically significant (Yes NCS) for laboratory parameters.

All laboratory data will be listed.

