Data extracted: DD.MM.YYYY

ML39355_STATISTICAL ANALYSIS PLAN_Final 2.0_17 June 2020
Pregnancies

F. Hoffmann-La Roche Ltd
 ML39355
Table 3.15 Urine pregnancy test
 Treated set (TS)
 Page X of X

	Total (N = XX) n (%)
Screening	
n'	XX
Done [1]	XX (XX.X)
Negative [2]	XX (XX.X)
Positive [2]	XX (XX.X)
Not Done [1]	XX (XX.X)
Male subject [1]	XX (XX.X)
Female subject with no childbearing potential [1]	XX (XX.X)
Other [1]	XX (XX.X)
Day 1	
n'	XX
Done [1]	XX (XX.X)
Negative [2]	XX (XX.X)
Positive [2]	XX (XX.X)
Not Done [1]	XX (XX.X)
Male subject [1]	XX (XX.X)
Female subject with no childbearing potential [1]	XX (XX.X)
Other [1]	XX (XX.X)
...	
...	...

N: the number of women of childbearing potential in the TS. n' - the number of valid observations.

n: the number of patients within a specific category.

[1] Percentages are based on the corresponding number of valid observations.

[2] Percentages are based on the number of patients for whom the pregnancy test was performed.

Path to the program code, date and time of output

Data extracted: DD.MM.YYYY

<The following Urine pregnancy test assessments will be presented: Screening, Day 1, Week 4, Week 8, Week 12, Week 20, Week 26 Day 2>

ML39355_STATISTICAL ANALYSIS PLAN_Final 2.0_17 June 2020
Laboratory tests

 F. Hoffmann-La Roche Ltd
 ML39355

Table 3.16 Hematology. Descriptive statistics

Treated set (TS)

Page X of X

Parameter: XXXXXXXXXXXXXXXXXXXX, <units>

	Total (N = XX)	Change from the baseline
Screening		
n	XX	
Mean	XX.X	
SD	XX.XX	
Median	XX.X	
Min	XX	
Max	XX	
Day 1		
n	XX	
Mean	XX.X	
SD	XX.XX	
Median	XX.X	
Min	XX	
Max	XX	
Baseline		
n	XX	
Mean	XX.X	
SD	XX.XX	
Median	XX.X	
Min	XX	
Max	XX	
Week 2		
n	XX	XX
Mean	XX.X	XX.X
SD	XX.XX	XX.XX
Median	XX.X	XX.X
Min	XX	XX
Max	XX	XX

ML39355_STATISTICAL ANALYSIS PLAN_Final 2.0_17 June 2020

...

...

...

N: the number of patients in the Treated set (TS).
n: the number of valid measurements.

The baseline value for a variable is defined as the last non-missing value collected before the first study drug administration.
<The following assessments will be presented: Screening, Day 1, Baseline, Week 2, Week 4, Week 8, Week 16, Week 20, Week 26 Day 2, Follow-up visit, Week 39, Week 52>
<The following parameters will be presented: Leukocytes ($10^9/L$), Erythrocytes ($10^{12}/L$), Hemoglobin (g/L), Hematocrit (L/L), Platelets ($10^9/L$), Neutrophils/Leukocytes (%), Eosinophils/Leukocytes (%), Basophils/Leukocytes (%), Monocytes/Leukocytes (%), Lymphocytes/Leukocytes (%).>

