Path to the program code, date and time of output

Data extracted: DD.MM.YYYY

ML39355_STATISTICAL ANALYSIS PLAN_Final 2.0_17 June 2020

Similar to table 3.16, the following tables will be constructed:

F. Hoffmann-La Roche Ltd
ML39355

Table 3.17 Blood chemistry. Descriptive statistics

Treated set (TS)

Page X of X

<The following parameters will be presented: Albumin (g/L), Alkaline Phosphatase (U/L), Alanine Aminotransferase (U/L), Aspartate Aminotransferase (U/L), Direct bilirubin (umol/L), Bilirubin (umol/l), Protein (g/L), Cholesterol (mmol/L), Creatine Kinase (U/L), Creatinine (umol/L), Triglycerides (mmol/L), Gamma Glutamyl Transferase (U/L), Glucose (mmol/L), Lactate Dehydrogenase (U/L), Calcium (mmol/L), Phosphate (mmol/L), Magnesium (mmol/L), Potassium (mmol/L), Sodium (mmol/L), Urea nitrogen (mmol/L), Urate (umol/L), Creatinine Clearance (mL/min).>

ML39355_STATISTICAL ANALYSIS PLAN_Final 2.0_17 June 2020

 F. Hoffmann-La Roche Ltd
 ML39355

Table 3.18 Hematology. Shift table

Treated set (TS)

Page X of X

Parameter: XXXXXXXXXXXXXXXXXXXX, <units>

	Baseline			Total
	Low	Normal	High	
Baseline				
Low				XX (XX.X)
Normal				XX (XX.X)
High				XX (XX.X)
Total				XX (100)
Week 2				
Low	XX (XX.X)	XX (XX.X)	XX (XX.X)	XX (XX.X)
Normal	XX (XX.X)	XX (XX.X)	XX (XX.X)	XX (XX.X)
High	XX (XX.X)	XX (XX.X)	XX (XX.X)	XX (XX.X)
Total	XX (XX.X)	XX (XX.X)	XX (XX.X)	XX (100)
Week 4				
Low	XX (XX.X)	XX (XX.X)	XX (XX.X)	XX (XX.X)
Normal	XX (XX.X)	XX (XX.X)	XX (XX.X)	XX (XX.X)
High	XX (XX.X)	XX (XX.X)	XX (XX.X)	XX (XX.X)
Total	XX (XX.X)	XX (XX.X)	XX (XX.X)	XX (100)
...				
...

The baseline value for a variable is defined as the last non-missing value collected before the first study drug administration. Percentages are based on the number of patients with a non-missing assessment at the corresponding time point and at baseline.

<The following assessments will be presented: Baseline, Week 2, Week 4, Week 8, Week 16, Week 20, Week 26 Day 2, Follow-up visit, Week 39, Week 52>

Path to the program code, date and time of output

Data extracted: DD.MM.YYYY

ML39355_STATISTICAL ANALYSIS PLAN_Final 2.0_17 June 2020

Similar to table 3.18, the following tables will be constructed:

F. Hoffmann-La Roche Ltd
ML39355
Table 3.19 Blood chemistry. Shift table
Treated set (TS)
Page X of X

ML39355_STATISTICAL ANALYSIS PLAN_Final 2.0_17 June 2020

 F. Hoffmann-La Roche Ltd
 ML39355

Table 3.20 Hematology. Out of range. Frequency table

Treated set (TS)

Page X of X

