Page X of X

Parameter: XXXXXXXXXXXXXXX, <units>

	Total (N = XX) n (%)
Screening	
n'	XX
Normal	XX (XX.X)
Out of Range NCS	XX (XX.X)
Out of Range CS	XX (XX.X)
Day 1	
n'	XX
Normal	XX (XX.X)
Out of Range NCS	XX (XX.X)
Out of Range CS	XX (XX.X)
Baseline	
n'	XX
Normal	XX (XX.X)
Out of Range NCS	XX (XX.X)
Out of Range CS	XX (XX.X)
Week 2	
n'	XX
Normal	XX (XX.X)
Out of Range NCS	XX (XX.X)
Out of Range CS	XX (XX.X)
...	
...	...

N: the number of patients in the Treated set (TS). n' - the number of valid observations.

n: the number of patients within a specific category. Percentages are based on the corresponding number of valid observations.

ML39355_STATISTICAL ANALYSIS PLAN_Final 2.0_17 June 2020

Path to the program code, date and time of output

Data extracted: DD.MM.YYYY

<Report all parameters: Systolic blood pressure, mm Hg/ Diastolic blood pressure, mm Hg/ Pulse rate, beats/minute/ Respiratory rate, breaths/minute/
Axillary temperature, C>
<The following assessments will be presented: Screening, Day 1, Baseline, Week 2, Week 4, Week 8, Week 16, Week 20, Week 26 Day 1, Week 26 Day 2,
Follow-up visit, Week 39, Week 52>

ML39355_STATISTICAL ANALYSIS PLAN_Final 2.0_17 June 2020
Weight

 F. Hoffmann-La Roche Ltd
 ML39355

Table 3.24 Weight. Descriptive statistics

Treated set (TS)

Page X of X

Parameter: Weight, kg

	Total (N = XX)	Change from the baseline
Screening		
n	XX	
Mean	XX.XX	
SD	XX.XXX	
Median	XX.XX	
Min	XX.X	
Max	XX.X	
Day 1		
n	XX	
Mean	XX.XX	
SD	XX.XXX	
Median	XX.XX	
Min	XX.X	
Max	XX.X	
Baseline		
n	XX	
Mean	XX.XX	
SD	XX.XXX	
Median	XX.XX	
Min	XX.X	
Max	XX.X	
Week 2		
n	XX	XX
Mean	XX.XX	XX.XX
SD	XX.XXX	XX.XXX
Median	XX.XX	XX.XX
Min	XX.X	XX.X
Max	XX.X	XX.X

ML39355_STATISTICAL ANALYSIS PLAN_Final 2.0_17 June 2020

...

...

...

N: the number of patients in the Treated set (TS).
n: the number of valid measurements.

The baseline value for a variable is defined as the last non-missing value collected before the first study drug administration.

Path to the program code, date and time of output

Data extracted: DD.MM.YYYY

<The following assessments will be presented: Screening, Day 1, Baseline, Week 2, Week 4, Week 8, Week 16, Week 20, Week 26 Day 2, Follow-up visit>

ML39355_STATISTICAL ANALYSIS PLAN_Final 2.0_17 June 2020
ECG

 F. Hoffmann-La Roche Ltd
 ML39355

Table 3.25 ECG. Descriptive statistics

Treated set (TS)

Page X of X

Parameter: XXXXXXXXXXXXXXXX, <units>

	Total (N = XX)	Change from the baseline
Screening		
n	XX	
Mean	XX.X	

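### The printed Cockcroft-Gault formula behind the renal exclusion has no sex term and no brackets, and the SAP tabulates clearance at two visits with no scheduled weight

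*Protocol*

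**What the plan says.** Exclusion 23 in Protocol 4.1.2 reads "Creatinine clearance < 30 mL/min, calculated using the Cockcroft-Gault formula" and refers the reader to Section 4.5.8. That section places the calculation at Screening: "Creatinine clearance should be assessed at the Screening for eligibility confirmation using the following formula by Cockcroft-Gault". It prints two versions, one for serum creatinine in mg/dL (constant 72) and one for µmol/L (constant 0.81). Both multiply (140 − age) × weight by 1.0, then show a division sign, the constant and × serum creatinine, with no brackets. SAP 9.4 reprints both versions unchanged.

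Neither document gives a version for women, although Protocol 4.1.1 admits "Male and female patients aged 40–80 years". The protocol does give separate equations for men and women elsewhere: haemoglobin-corrected DLco in 4.5.7 and predicted DLco in 4.5.11.3.

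SAP 9.4 repeats the Screening sentence but also plans "descriptive statistics of measured values and changes from baseline (including creatinine clearance" among its laboratory tables. Clearance is a listed parameter of Table 3.17, which is built on the layout of Table 3.16. The visits of Table 3.16 end with "Week 26 Day 2, Follow-up visit, Week 39, Week 52". The visit list for weight in Table 3.24 ends earlier: "Week 16, Week 20, Week 26 Day 2, Follow-up visit".

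**The concern.** A factor of exactly 1.0 has no effect, so its presence suggests that one branch of a sex-dependent factor was kept and the other dropped. If so, the screening rule is more lenient for women than the named method, at the only numeric renal cut-off in the eligibility criteria (exclusion 14 covers only end-stage disease on dialysis).

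The missing brackets matter because the SAP is what the programmer works from. Taken literally from left to right, the expression multiplies by creatinine instead of dividing by it.

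The third matter is independent of the first two. Clearance needs a weight. If none is taken at Weeks 39 and 52, the planned values and changes from baseline there either cannot be produced or depend on an undocumented choice of weight.

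**Working it through.** Neither document states a computed clearance, so there is no figure of the plan's own to reproduce.

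**1. Do the two printed versions agree, and under which reading?** The inputs are the constants 72 and 0.81 from Protocol 4.5.8. Assumption: 88.4 µmol/L per mg/dL, a unit conversion that the documents do not give.

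- With creatinine in the denominator, the µmol/L constant should be 72/88.4 = 0.814, against 0.81 as printed. These differ by 0.6%, so the versions agree and the constants do not compensate for the 1.0.
- Illustrative patient: 75 years, 60 kg, creatinine 2.5 mg/dL (2.5 × 88.4 = 221 µmol/L). (140 − 75) × 60 = 3900.
- Bracketed: 3900/(72 × 2.5) = 21.7 and 3900/(0.81 × 221) = 21.8 mL/min.
- Left to right: 3900/72 × 2.5 = 135 and 3900/0.81 × 221 = 1,064,074 mL/min. Clearance rises with creatinine, and the two versions contradict each other.

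Only the bracketed reading is coherent.

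**2. What would a female factor change?** Let f be the factor for women in the cited formula. It is not in the documents; 0.85 is assumed, with a range of 0.80 to 0.90. The overstatement is 1/f − 1. Printed values from 30 up to 30/f would fall below 30. The last column is an illustrative woman of 75 years, 60 kg, creatinine 150 µmol/L, whose printed value is 3900/(0.81 × 150) = 32.1 mL/min.

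| f | Overstatement | Printed values that fall below 30 | Example, 32.1 × f |
|---|---|---|---|
| 0.80 | 25.0% | 30 up to 37.5 | 25.7 |
| 0.85 | 17.6% | 30 up to 35.3 | 27.3 |
| 0.90 | 11.1% | 30 up to 33.3 | 28.9 |

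The example passes exclusion 23 as printed and falls below 30 at every f in the range.

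A constant f multiplies a woman's baseline and later values alike, so her percentage change is unaffected. Her absolute change is scaled by the same factor.

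**3. Weight at Weeks 39 and 52.**

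- Protocol 4.5.13.10 lists physical examination, vital signs and chemistry at both visits, but no weight. Section 4.5.13.9 does list weight at the Follow-up visit.
- The height/weight row of the schedule in Appendix 1 has no mark at either visit.
- Protocol 4.5.5 defines vital signs without weight.
- SAP Table 3.24 stops at the Follow-up visit, whereas Table 3.17 takes on Weeks 39 and 52 from Table 3.16.
- The SAP has no rule for which weight enters the formula.

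For a patient whose last scheduled weight is at Week 26, that weight is 39 − 26 = 13 weeks old at Week 39 and 52 − 26 = 26 weeks old at Week 52, before visit windows. If it were used and true weight had fallen by 5%, clearance would be overstated by 1/0.95 − 1 = 5.3%; after a 10% fall, by 1/0.90 − 1 = 11.1%. Both weight changes are illustrative. Protocol 5.1.1.5 names weight loss as a risk of pirfenidone.

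**The case against.** The strongest objection is that no female factor appears in either document and the cited paper is not available here. A reader might infer that clearance in women is overstated by 18% as a matter of fact. The documents do not support that. They show a multiplier with no effect and no sex term; the size depends on an assumed f. This objection stands, and it is why the figures carry a range and the remedy is a check against the source.

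A reader might also infer that women admitted in the affected band are protocol deviations. They are not: exclusion 23 points to Section 4.5.8, and a woman who passes the printed formula met the protocol as written.

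On the brackets, it can be said that a fraction may have been flattened when the text was extracted, and that a left-to-right result above a million in µmol/L, the unit used for creatinine in Table 3.17, would be noticed at once. Both are fair, so an actual programming error is unlikely. Still, Section 4.5.7 of the same extracted protocol brackets its denominator, and the mg/dL misreading (135 mL/min) is not absurd on its face.

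On Weeks 39 and 52, a reader might infer that the reported values must be biased upward. That does not follow. The SAP has no carry-forward rule for weight or laboratory data, and the Table 3.16 layout counts valid measurements, so the rows may simply be empty. Weight may also be recorded unscheduled: SAP 9.5 and Listing 32 handle it together with vital signs, which are taken at both visits. What stands is that the plan schedules an output without scheduling its input.

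**Conclusion.** The point holds on three matters shown by the documents alone: a formula behind a renal safety cut-off with an inert multiplier and no provision for women, an unbracketed denominator, and a clearance summary at two visits with no scheduled weight and no rule for choosing one.

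The size of the first is conditional. With an assumed f of 0.85 it is a 17.6% overstatement in women, and eligibility would change only for women with printed values from 30 up to 35.3 mL/min; over f from 0.90 to 0.80 the overstatement runs from 11.1% to 25.0%. How many enrolled women lie in that band is unknown. If the cited formula has no sex term, the screening consequence disappears.

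The documents also give no ground for saying that every summary for women is distorted: Table 3.17 is not split by sex, and percentage change within a woman is untouched. The consequences are confined to renal eligibility and one safety table, but they are worth correcting because the cut-off protects patients and the correction is small.

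**What to change.** - Check the printed formula against the cited source, then reconcile Protocol 4.5.8, SAP 9.4 and exclusion 23. Print the formula with the constant and creatinine bracketed together in the denominator, and with any sex term explicit. Which factor applies, if any, is for the sponsor to settle from the source; the 30 mL/min threshold is not in question here.
- If a sex term applies, recompute screening clearance for enrolled women from the stored age, weight and creatinine, and list any value below 30 for safety review, not as a protocol deviation.
- Limit the clearance rows of Table 3.17 to visits with a scheduled weight, which removes Weeks 39 and 52.

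The cost is a few lines of text in two documents, one derivation and a shortened visit list. The recomputation needs no new data, since age, weight and creatinine are all scheduled at Screening.

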4.5.9 Electrocardiograms

Single ECG recordings will be obtained at specified timepoints, as outlined in the schedule of activities (see [Appendix 1](#)), and may be obtained at unscheduled timepoints as indicated.

All ECG recordings must be performed using a standard high-quality, high-fidelity digital electrocardiograph machine equipped with computer-based interval measurements. Lead placement should be as consistent as possible. ECG recordings must be performed after the patient has been resting in a supine position for at least 10 minutes. All ECGs are to be obtained prior to other procedures scheduled at that same time (e.g., vital sign measurements, blood draws, *bronchodilator test*) and should not be obtained within 3 hours after any meal. Circumstances that may induce changes in heart rate, including environmental distractions (e.g., television, radio, conversation) should be avoided during the pre-ECG resting period and during ECG recording.

For safety monitoring purposes, the investigator must review, sign, and date all ECG tracings. Paper and digital copies of ECG tracings will be kept as part of the patient's permanent study file at the site. The following should be recorded in the appropriate eCRF: heart rate, RR interval, QRS interval, PR duration, uncorrected QT interval, and QT interval corrected for heart rate using Fridericia's method (QTcF) based on the machine readings of the individual ECG tracings. Any morphologic waveform changes or other ECG abnormalities must be documented on the eCRF. If considered appropriate by the Sponsor, ECGs may be analyzed retrospectively at a central laboratory.

If at a particular postdose timepoint the QTcF is > 500 ms and/ or > 60 ms longer than the baseline value, another ECG must be recorded, ideally within the next 5 minutes or in the utmost 24 hours, and ECG monitoring should continue until QTcF has stabilized on two successive ECGs. The Medical Monitor should be notified. Standard-of-care treatment may be instituted per the discretion of the investigator. A decision on study drug discontinuation should be made, as described in [Section 5.1.2](#). The investigator should also evaluate the patient for potential concurrent risk factors (e.g., electrolyte abnormalities, co-medications known to prolong the QT interval, severe bradycardia).

4.5.10 6-Minute Walk Test

The 6MWT measures the distance *in meters* that a patient can walk at his/her own pace on a measured, flat hard surface in a period of 6 min. The 6MWT assesses the global and integrated responses of all body systems involved during walking. The 6MWT based

Pirfenidone—F. Hoffmann-La Roche Ltd

on ATS recommendations (ATS 2002) will be performed as outlined in the Reference Guide.

